9.4.3 ANALYSIS OF THE SECONDARY ENDPOINT(S)

We will use linear mixed models to explore the impact of the intervention on staff satisfaction and family burden. The models will be specified with fixed effects for the intervention and time and random effects for facility, facility*time, and participant (**RC-4**). For staff satisfaction, the participant is

the staff member. For each staff member we will measure satisfaction at baseline and at least one measurement per time-period. For family burden, the participant is the family member/caregiver. We will measure family burden at baseline and at least one measurement per time-period the resident is enrolled in the study. These random effects account for correlation among individuals in the same cluster at the same time point, correlation between observations for the same individual at two time points, and the correlation between two means of the same cluster at two time points. We will estimate the mean difference and corresponding 95% confidence interval for the intervention effect.

9.4.4 SAFETY ANALYSES

N/A

9.4.5 BASELINE DESCRIPTIVE STATISTICS

We will compare facilities at baseline and the last time period on several characteristics including: number of residents with measured hearing loss, gender composition, age range, race and ethnicity of residents, total occupancy, and annual staff turnover. We will also compare them on the following measures from the previous 5 months: number of unexpected hospitalizations, number of falls, number of residents moving to a higher level of care, and number of deceased residents.

9.4.6 PLANNED INTERIM ANALYSES

N/A

9.4.7 SUB-GROUP ANALYSES

In an effort to ascertain whether the intervention is more or less effective for certain resident subgroups (**RQ-4, HT-1**), we will explore the following groups (**HT-2**):

(a) those who have different degrees of hearing loss at baseline (~84% expected to have some level of hearing loss) and those who do not;

H_1 The intervention provided by the Engage Model and measured by the HHIE and Satisfaction with Participation will have more impact on residents with hearing loss at baseline as compared to residents with no measured hearing loss.

H_0 The intervention provided by the Engage Model and measured by the HHIE and Satisfaction with Participation will not have a different impact on residents with hearing loss at baseline as compared to residents with no measured hearing loss.

(b) those who have different degrees of hearing loss and use a device (~18-32% of 84%; note these are estimates and the actual percent of device use will be used) compared to those who do not use a device but have different degrees of hearing loss;

H_1 The intervention provided by the Engage Model and measured by the HHIE and Satisfaction with Participation will have more impact on residents with hearing loss who do not use a hearing device at baseline as compared to residents with hearing loss who do use a hearing device.

H_0 The intervention provided by the Engage Model and measured by the HHIE and Satisfaction with Participation will not have a different impact on residents with hearing loss who do not use a hearing device at baseline compared to residents with hearing loss who do use a hearing device.

(c) those with high social participation at baseline (~50%) and those with lower social participation;

H_1 The intervention provided by the Engage Model and measured by Social Participation will have more impact for residents with low social participation at baseline compared to residents with normal or high social participation.

H_0 The intervention provided by the Engage Model and measured by Social Participation will not have a different impact for residents with low social participation at baseline compared to residents with normal or high social participation.

(d) those with high hearing-specific HRQoL (~50%) and those with lower hearing-specific HRQoL. Scores of 0-8 on the HHIE are “low” and 10-40 are “high” with 10% indicating a significant change.⁸³

H_1 The intervention provided by the Engage Model and measured by HHIE will have more impact for residents with high hearing-specific HRQoL at baseline as compared to residents with hearing-specific HRQoL within normal limits.

H_0 The intervention provided by the Engage Model and measured by HHIE will not have a different impact for residents with high hearing-specific HRQoL at baseline as compared to residents with hearing-specific HRQoL within normal limits.

The individual hearing threshold data will allow us to stratify according to hearing levels. We will use the ASHA classification of degrees of hearing loss (normal -10 to 15; slight 16 to 25; mild 26 to 40; moderate 41 to 55; moderately severe 56 to 70; severe 71 to 90; profound >91 dB).⁸⁴ The number of individuals in the HHIE subgroups and hearing level subgroups cannot be adequately estimated and will be known when data collection are complete. We will explore the heterogeneity using interaction terms (**HT-3**) between the factor of interest and the intervention fixed effect. Regardless of the significance, we will estimate the treatment effect for each subgroup with corresponding 95% confidence intervals (**HT-2**).

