Five pairs of 10 facilities will be assigned the intervention (Engage Model, gray cells) randomly over the course of 28 months with the first 4 months used as a baseline period (total data collection period is 28 months).⁸¹ Residents enrolled in the study during any time period will be followed until the end of the study or until they are no longer a resident of the facility, whichever comes first. This implies that crossover to the intervention is not only at the facility level but also the resident level.⁷⁵ Once the intervention is available at a facility, residents will be exposed to the intervention continuously. The resident level outcomes of satisfaction with social participation and hearing-specific HRQoL will be measured every 5 months for the duration of the study.

	Baseline (4 months)	Time 1 (5 months)	Time 2 (5 months)	Time 3 (5 months)	Time 4 (5 months)	Time 5 (5 months)
Facility 1-2	60					60
Facility 3-4	60					60
Facility 5-6	60					60
Facility 7-8	60					60
Facility 9-10	60					60

Randomization and Allocation: The stepped wedge design implies a baseline period, in which no clusters are exposed to the intervention.⁷⁹ Then, at the chosen time interval, two facilities will be randomized to cross from the control to intervention. This process continues until all ten facilities have crossed over to the intervention.

Percent of Total Data Collected by this Date													
	0%	4 months	17%	5 months	34%	5 months	51%	5 months	68%	5 months	85%	5 months	100%
6/1/2021	Baseline	9/1/2021	Time 1	2/1/2022	Time 2	7/1/2022	Time 3	12/1/2022	Time 4	5/1/2023	Time 5		10/1/2023
Facilities 1-2													
Facilities 3-4													
Facilities 5-6													
Facilities 7-8													
Facilities 9-10													
	Consult Model												
	Engage Model												

The order of this cross over process will be randomized. We will randomize 2 facilities to switch from the control to intervention at each step using SAS version 9.4 (**RC-5**). The statistician will communicate the sequence to the Study Team for intervention implementation preparation (**IR-2**). If the expected number of individuals across the 10 facilities are not recruited in a timely manner we will expand to other Assisted Living/Personal Care Facilities at UPMC. Triggers for expanded recruitment will include 1) lower census in the building than targeted (10% lower than expected) and/or 2) inability to meet enrollment milestones over two check points as outlined on the Milestone chart.

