9.2 SAMPLE SIZE DETERMINATION

We used a method to estimate sample size that takes into account the cluster randomization, the stepped wedge design, and the longitudinal data on residents⁸⁴ (**RC-3**). Our study design originally included 8 clusters (facilities) with 5 time periods (including the baseline), 4 steps, 2 facilities switching from control to intervention at each step, and an average of 65 residents per facility

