being continuously followed (**CI-2**). We expect some residents to leave the facility for different reasons and our design will allow new residents to contribute data from the time of moving into the facility until the end of the study period. We conducted sample size analyses accounting for intracluster correlation ($\rho=0.20$) (**RC-3**), individual autocorrelation ($\tau=0.5$), and cluster autocorrelation ($\pi=0.9$)⁸⁴. The *intracluster correlation* is a measure of correlation among residents measured at the same facility within the same time frame. Cluster randomized trials typically assume values between 0.01-0.10 with higher values indicating more similarity in outcomes within clusters such as schools, primary care clinics, or providers. We assumed a higher correlation given that residents are living within the same quarters and sharing the same residential experience. The *individual autocorrelation* is the correlation between any two measures within the same resident over time. We conservatively assumed this to be 0.5 as a lower bound because repeated measures within person are often highly correlated. The *cluster autocorrelation* is the correlation between two population means from the same cluster at different times. We assumed this would be very high (0.9) given the stability of the population in the facilities over time. This design achieves 80% power to detect the hypothesized effect size of 0.3 for either primary outcome (satisfaction with participation or hearing-specific health-related quality of life) between control and intervention periods (two-sided, $\alpha=0.025$ for each outcome). An effect size of 0.3 translates to a difference between groups of 3 points on the satisfaction with communication scale assuming a standard deviation between 9 and 10 based on our preliminary data from local facilities. An effect size of 0.3 translates to a difference between groups of 3.6 points on the hearing-specific health-related quality of life measure assuming a standard deviation of 12 based on our preliminary data from local facilities. These differences are considered clinically meaningful. We believe this hypothesized effect exists because of previous literature using these measures in clinical populations and from our pilot data.^{62,64}

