9.4.2 ANALYSIS OF THE PRIMARY ENDPOINT(S)

We will use linear mixed models to test the hypothesis of improving satisfaction with participation and hearing-specific HRQoL specifying the fixed effects of intervention and time and random effects for facility, facility*time, and resident (**RC-4**). These random effects are based on the statistical model referenced in Hooper (2016)⁸¹ that account for the correlation among individuals in the same cluster at the same time point, correlation between observations for the same individual at two time points, and the correlation between two means of the same cluster at two time points. Time will be treated as a categorical variable. We will estimate the mean difference and corresponding 95% confidence interval for the intervention effect (**IR-1**) and test that the difference between intervention and control conditions is significant. A two-sided test $\alpha=0.025$ for each outcome using a Wald t-test with Kenward Roger correction for small sample bias and Satterthwaite degrees of freedom will be employed. Primary analysis will be unadjusted for covariates.

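### Subgroups (c) and (d) are split on the baseline value of the outcome being tested; as written, regression to the mean would appear as a subgroup effect of Engage

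*Combined protocol and SAP*

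**What the plan says.** Section 9.4.7 lists four exploratory subgroup comparisons. Item (c) contrasts "those with high social participation at baseline (~50%) and those with lower social participation", with social participation as the outcome; the only such instrument listed in section 8.1 is the satisfaction scale. Item (d) contrasts "those with high hearing-specific HRQoL (~50%) and those with lower hearing-specific HRQoL", with HHIE as the outcome. Heterogeneity is examined through interactions "between the factor of interest and the intervention fixed effect", and each subgroup's effect is to be reported with a 95% confidence interval whether or not the interaction is significant.

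The only resident-level model is in section 9.4.2: "specifying the fixed effects of intervention and time and random effects for facility, facility*time, and resident". Time is categorical. "Primary analysis will be unadjusted for covariates".

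Section 9.2 counts the baseline among the time periods, and section 4.1 states: "The stepped wedge design implies a baseline period, in which no clusters are exposed to the intervention". Nothing in the document removes the classifying score from the response, adjusts for it, or lets time trends differ by subgroup. Section 9.4.1 refers to a full SAP as a separate document, which was not among the documents reviewed.

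**The concern.** Read together, sections 9.4.2 and 9.4.7 use the Baseline score twice: to assign the subgroup, and as an all-Consult response. A resident's score varies around his or her usual level, so the low group contains people who were low by chance and the high group people who were high by chance. At later visits the groups move towards each other with no help from the intervention. The common time effect cannot absorb this, because the two groups move in opposite directions. Engage occurs only after Baseline, so the movement loads onto the subgroup-by-intervention term.

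The bias favours low-satisfaction residents in (c) and high-handicap residents in (d), the direction of both alternative hypotheses. It would therefore look like confirmation, and the promised subgroup estimates and intervals would carry it too.

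A smaller point: (d) labels HHIE scores of 10 to 40 as high hearing-specific HRQoL, whereas section 6.1.2 says that higher scores mean more handicap. The numeric cut makes the intended contrast recoverable, but the label is reversed.

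**Working it through.** **Inputs (section 9.2).** Intracluster correlation 0.20, cluster autocorrelation 0.9, individual autocorrelation 0.5, effect 0.3 SD, 7.5% loss per period. Current design: 10 facilities, 5 steps of 2 facilities, 30 residents each, so 6 periods with Baseline. The interaction is tested at 0.05 (9.4.1).

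**The plan's own figure.** For the original 8 facilities of 65 residents over 5 periods, a cohort stepped-wedge model with Baseline as a modelled period gives 80.2% power at two-sided 0.025, using a noncentral t with 8×5 − 8 − 5 = 27 df (stated: 80%). The normal approximation gives 84.2%. With 7.5% churn the t version gives 79.1% (stated: 77-79%). The model and inputs are therefore read correctly.

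**Size by hand.** Two scores from one resident correlate r = 0.20×0.9 + 0.80×0.5 = 0.58. A median split of a normal score puts the halves 2√(2/π) = 1.60 SD apart at Baseline and 1.60×0.58 = 0.93 SD apart at every later visit. The gap lost is 1.60×(1 − r) = 0.67 SD, with no treatment effect.

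A facility crossing at Time s (s = 1 to 5) spends (6 − s)/6 of its periods on Engage. In a within-resident regression the Baseline change enters with weight (6 − s)/6, summing to 15/6. The denominator is s(6 − s)/6, summing to 35/6. The share credited to Engage is 15/35 = 0.43, so the false interaction is about 0.67×0.43 = 0.29 SD. This ignores churn and between-resident information.

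**Simulation.** Null effect in everyone, about a 50% split, 7.5% loss per period, only residents with a Baseline-period score analysed, REML with the random effects of 9.4.2, Wald test at 1.96, 1,000 trials per row. Individual autocorrelations above 0.5 are assumptions.

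| Individual autocorrelation | r | 1.60(1 − r) × 15/35 | Simulated interaction (SD) | Points at SD 10 | Rejected at 0.05 |
|---|---|---|---|---|---|
| 0.5 | 0.58 | 0.29 | 0.303 | 3.0 | 97.5% |
| 0.65 | 0.70 | 0.21 | 0.217 | 2.2 | 90.9% |
| 0.775 | 0.80 | 0.14 | 0.143 | 1.4 | 76.8% |
| 0.8875 | 0.89 | 0.08 | 0.074 | 0.7 | 47.7% |

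All rejections were in the same direction. With a true effect of 0.3 SD in everyone, the model shows 0.455 (low) and 0.148 (high) at r = 0.58, about 4.5 and 1.5 points instead of 3.0 in both. At r = 0.89 it shows 0.337 and 0.263.

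**Cause.** Splitting on each resident's true level instead of the Baseline score gives 0.00 SD and 6.0% rejection. Classifying everyone, newcomers included, by their first score still gives 0.31 SD and 99% rejection at r = 0.58.

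**Bounded HHIE.** Assumptions: latent SD 12, even scores clipped to 0-40, 25 residents per facility (84% of 30), 35%, 50% or 64% at or above 10; 500 trials each. The false difference is 3.2-3.4 points (92-96% rejected) at autocorrelation 0.5, 1.6-1.7 (70-75%) at 0.775, and 0.9 (45-55%) at 0.8875.

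**Remedies under the null.**

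| Setting | Drop Baseline row | Keep it, add subgroup-by-time |
|---|---|---|
| Constant correlation | within 0.002 SD of zero; 4.8-5.8% rejected | 0.003 SD; 5.8-6.7% |
| Lag-1 of 0.5, falling 10% per period | +0.125 SD; 28% | within 0.005 SD of zero; 7.5% |
| Lag-1 of 0.5, falling 20% per period | +0.214 SD; 57% | within 0.005 SD of zero; 8.3% |
| Lag-1 of 0.8, falling 5% per period | +0.117 SD; 42% | within 0.005 SD of zero; 6.5% |

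The decay rates are assumptions. For bounded HHIE both remedies cut the mean bias to at most 0.12 points. Rejection is then 4-8% with 50% or 64% above the cut, but 10-16% with 35% above it, where floor effects make the model standard error too small.

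**The case against.** - **Unseen SAP.** Section 9.4.7 gives one sentence of method and does not say which rows are responses or whether time may differ by subgroup. The no-covariate rule in 9.4.2 governs the primary analysis only. The separate SAP could specify a sound model. This stands: the point concerns the text as written and is partly an inference.
- **The largest figure uses the lowest correlation.** On its individual autocorrelation of 0.5, the plan says: "We conservatively assumed this to be 0.5 as a lower bound because repeated measures within person are often highly correlated". This also stands. The size is best given as 0.07 to 0.30 SD, but even the low end rejects about half the time at a nominal 5%.
- **HHIE points.** Clipping a latent SD of 12 to 0-40 leaves an observed SD of 8.4 to 10.5, so those values are illustrative and should not be set directly against the plan's 3.6-point difference. The bias remains.
- **Cost of the remedy.** Subgroup-by-time terms multiply the interaction variance by (0.113/0.076)² = 2.2. The interaction detectable with 80% power becomes about 2.8×0.113 = 0.32 SD, as large as the whole design effect. Under the constant correlation that the plan assumes, dropping the Baseline row suffices at less cost. Preferring the costlier remedy is a judgement about decay.
- **Population.** Classifying by the Baseline period leaves out newcomers, whereas section 9.3 includes all enrolled residents. That exception should be stated.
- **Standing of the analyses.** They are exploratory, involve two of four subgroup comparisons, and leave the primary tests alone. That limits the severity but does not excuse a bias foreseeable before analysis.

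**Conclusion.** The concern holds. Followed as written, the analyses for (c) and (d) produce a false subgroup difference in the hypothesised direction when the effect of Engage is the same in everyone or zero. It runs from about 0.30 SD at the plan's correlations to 0.07 SD at a within-resident correlation of 0.89, with rejection from 97.5% down to 48%.

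This rests on three assumptions: the Baseline score remains a response row, the two subgroups share one time trend, and the separate SAP does not say otherwise. The main figures also assume a normal outcome, a roughly even split and constant within-resident correlation.

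The primary analyses and subgroups (a) and (b) are not affected in this way. The HHIE label is an editorial correction and adds nothing to the severity. The subgroup model should be corrected before analysis.

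**What to change.** For (c) and (d) only, amend section 9.4.7 to:

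1. Keep all periods and add subgroup-by-categorical-time terms to the model. Removing the Baseline row from the response is an acceptable alternative only if within-resident correlation can be taken as constant over time.
2. State that these two analyses classify residents by their Baseline-period score only, as an exception to section 9.3.
3. In (d), describe HHIE 0-8 as little or no handicap and 10-40 as handicap (lower hearing-specific HRQoL), and word the hypotheses in terms of handicap.
4. If the separate SAP already does this, say so in 9.4.7.

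The cost is a short text change and one line of code, with no new data. At the plan's correlations the interaction standard error rises from 0.076 to 0.113 SD with subgroup-by-time terms, or to 0.092 SD if the Baseline row is dropped.

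Newcomers leave these two analyses. At 7.5% replacement over five intervals they number 5×0.075×30 = 11.25 per facility, or 11.25/41.25 = 27% of residents ever enrolled. The Baseline cohort supplies (1 − 0.925⁶)/0.075 = 4.98 of 6 assessments per place, so 17% of assessments are lost.

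If few residents score 10 or more on the HHIE, some excess rejection in (d) will remain, and its model-based standard error should be read with caution.

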9.4.8 TABULATION OF INDIVIDUAL PARTICIPANT DATA

N/A

9.4.9 EXPLORATORY ANALYSES

With respect to the effectiveness of the intervention, we believe there is a threshold of improvement with exposure to the intervention. In other words, there will be a change (i.e., improved hearing specific HR QoL and satisfaction with participation) and then that change will be maintained, it will not increase. However, with the data we will obtain, we will be able to explore if the change over 20 months relative to baseline is the same as the change at 5 months relative to baseline (dose effect within facilities), and the same incrementally for 15 or 10 months of exposure (pooling across facilities). These comparisons are exploratory as they are either completely or partially confounded with time. We also can conduct an analysis used in the depression trial⁸² to explore linear and quadratic terms for the number of periods in the intervention condition both at the facility and resident levels and the number of periods the resident was in the study.

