3 OBJECTIVES AND ENDPOINTS

OBJECTIVES	ENDPOINTS	JUSTIFICATION FOR ENDPOINTS
Primary		
Compare the effectiveness of a Consult Model versus an Engage Model in improving satisfaction with participation in social activities for all residents.	Satisfaction with Participation in Discretionary Social Activities – Short Form 7a V1.0	This is a measure with adequate psychometric data to support its use in identifying change in satisfaction with participation which is of primary interest when improving communication through hearing.
Compare the effectiveness of a Consult Model versus an Engage Model in increasing hearing-specific health-related quality of life (HRQoL) in residents with measured hearing loss.	Hearing Handicap Inventory for the Elderly (HHIE) – Screening V1.0	The HHIE is a reliable, valid measure of self-perceived hearing handicap. This is a direct measure of the intervention for individuals with hearing loss.
Secondary		
Compare the effectiveness of a Consult Model versus an Engage Model in increasing Staff Satisfaction.	Michigan Organizational Assessment Questionnaire (MOAQ)	This is a standardized measure of perceived stress by staff. Our previous stakeholders indicated that the staff questionnaire should be brief (3 questions).
Compare the effectiveness of a Consult Model versus an Engage Model in decreasing Family Burden.	Zarit Burden Interview - Modified 4 question V1.0	Reduction of burden is of interest in this study and the Zarit Burden Interview provides a standardized way to probe this outcome.

OBJECTIVES	ENDPOINTS	JUSTIFICATION FOR ENDPOINTS
Tertiary/Exploratory		
Define a threshold of improvement with exposure to the intervention	The HHIE and Satisfaction with Participation in Discretionary Social Activities will be used to assess threshold of improvement as a function of exposure to the Engage Model.	The two primary resident measures are of interest when defining a threshold or improvement over time.

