5.5 STRATEGIES FOR RECRUITMENT AND RETENTION

a. Facility Recruitment

The UPMC Senior Living Communities provide an opportunity to conduct intervention research. Within the 12 Assisted Living Facilities, we were able to collaborate with 7 facilities that have not experienced the Engage Model and currently have the Consult Model active. We included 3 non-UPMC facilities as well. These facilities were identified by the President of Senior Living as being appropriate to include in this study. We have existing relationships with all 10 facilities because two UPMC audiologists already provide the Consult Model of care in these facilities. These facilities have similar demographics of residents (age range, education, family caregivers, etc.), similar staff positions, years of experience, and responsibilities, similar physical layout, and similar week-to-week programming. This allows us to achieve the number of participants we need to complete the proposed intervention study. This coordinated system at UPMC also ensures that if there are any changes implemented in Senior Living during the investigation, they will be implemented across all facilities. For the three non-UPMC facilities, we will monitor any changes that might occur in these locations. The facilities also are geographically close to the University of Pittsburgh making intensive data collection (resident survey completion) practical.

b. Facility Retention

Sites that start the study are anticipated to complete the entire study and continue to participate for the full duration of the study. Throughout the study PI [name] will continue to maintain relationships with the Directors at each facility and be in communication with them regarding recruitment/research activities and to answer any questions/concerns the site may have. The Data Survey Coordinator, [name], will be in monthly contact with the facilities as well.

c. Resident, Family, and Staff Recruitment

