10.1.2 STUDY DISCONTINUATION AND CLOSURE

Given the current status of the Global Pandemic, this study could be suspended if the Assisted Living Facilities limit non-essential personnel (DCs) from entering the building due to safety concerns for residents. If this happens, the Study Team will notify the University of Pittsburgh IRB and PCORI. This disruption (implementing study questionnaires) will not have an adverse effect on residents, staff, and family. The Intervention (Consult and/or Engage) may not be disrupted depending on the Senior Living Community decision about continuing what may be viewed as essential care, but it could be limited in this same situation. The providers of the hearing care would work directly with the facility and the residents virtually in this case which would be independent of the research project.

The study would resume once concerns about safety of residents due to possible virus exposure were addressed.

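### Section 9.4.9 bases the exposure-threshold question mainly on changes from baseline confounded with calendar time, although an exposure-period model keeping categorical time can be fitted to the same data

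*Combined protocol and SAP*

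**What the plan says.** Section 3 lists a tertiary objective: "Define a threshold of improvement with exposure to the intervention". Section 9.4.9 expects an improvement that is then held and does not grow. It plans first to "explore if the change over 20 months relative to baseline is the same as the change at 5 months relative to baseline", as a within-facility comparison, and then to ask whether the change is "the same incrementally for 15 or 10 months of exposure (pooling across facilities"). It qualifies them: "These comparisons are exploratory as they are either completely or partially confounded with time".

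It adds, as an option, linear and quadratic terms for the number of intervention periods, "both at the facility and resident levels and the number of periods the resident was in the study", following a cited depression trial in nursing homes. It does not say whether that model includes calendar time. The primary model in section 9.4.2 treats time as categorical.

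The original design in section 9.2 had "5 time periods (including the baseline), 4 steps, 2 facilities switching from control to intervention at each step". The current one (sections 4.1 and 9.2) has ten facilities, a baseline and five follow-up periods, with two facilities crossing over at each of five steps.

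**The concern.** Within one facility, exposure length and calendar time advance together. A difference between the 20-month and 5-month changes therefore mixes growth or fading of the effect with anything else that changed over the intervening periods. The expected finding is a plateau, and drift could hide a plateau or imitate one. The section discloses the confounding but leaves it in the leading analysis, although the staggered crossover supplies a comparison without it: from Time 2 on, facilities with different exposure lengths are observed in the same calendar period.

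The stake is limited to the tertiary objective. No alpha depends on it.

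**Working it through.** **Inputs.** Section 9.2: ICC 0.20, cluster autocorrelation 0.9, individual autocorrelation 0.5, effect 0.3 SD, 30 residents per facility, ten facilities, five steps. Churn of 7.5% per period is stated for the eight-facility simulations and assumed here to carry over. With total variance 1:
- facility 0.20 × 0.9 = 0.18; facility-by-period 0.20 × 0.1 = 0.02;
- resident 0.80 × 0.5 = 0.40, with overlap 0.925^lag; residual 0.40.

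The method is generalised least squares on facility-period means with equal facility sizes.

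**The plan's own figure.** Section 9.4.9 states no power. For the primary effect the set-up gives SE 0.0861 and, at two-sided 0.025 with an assumed 20 to 25 df, power of 84.6 to 85.6%. Section 9.2 states 85%, so the set-up is a fair stand-in.

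**Estimability.** Exposure period of each pair by calendar period:

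| Pair | Base | T1 | T2 | T3 | T4 | T5 |
|---|---|---|---|---|---|---|
| 1 | 0 | 1 | 2 | 3 | 4 | 5 |
| 2 | 0 | 0 | 1 | 2 | 3 | 4 |
| 3 | 0 | 0 | 0 | 1 | 2 | 3 |
| 4 | 0 | 0 | 0 | 0 | 1 | 2 |
| 5 | 0 | 0 | 0 | 0 | 0 | 1 |

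Six period columns plus five exposure indicators have rank 11 of 11 (15 of 15 with fixed facility-pair effects and an intercept-free coding).

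**Bias of the within-facility contrast, period 4 v 1.** Baseline cancels, leaving the average of T4−T1 (pair 1) and T5−T2 (pair 2).
- Linear drift of d SD per period: bias 3d. For assumed d of 0.02, 0.05 and 0.10 this is 0.06, 0.15 and 0.30 SD. The documents give no drift value.
- Permanent step: in full if it starts at Time 3 or 4, by half at Time 2 or 5, not at all at Time 1.
- Shift confined to one period: −½ at Time 1 or 2, 0 at Time 3, +½ at Time 4 or 5.

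If the shift is common to all facilities, the time-adjusted contrast has bias 0 in every case.

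**Precision.** The within-facility variance for period k v 1 is [2(0.02) + 2(0.80 − 0.40 × 0.925^(k−1))/30] / [2(6 − k)]. For k = 4: (0.04 + 0.0322)/4 = 0.01806, so SE 0.134. All SEs, in SD units:

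| Period v 1 | Time-adjusted | Within facility | Pooled, no time | Increase over each |
|---|---|---|---|---|
| 2 | 0.094 | 0.093 | 0.089 | 1%, 5% |
| 3 | 0.117 | 0.108 | 0.100 | 8%, 17% |
| 4 | 0.153 | 0.134 | 0.118 | 14%, 30% |
| 5 | 0.215 | 0.192 | 0.159 | 12%, 35% |

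**Break-even drift, period 4 v 1.** Equal mean squared error requires (3d)² = 0.1533² − 0.1344², so d = 0.0737/3 = 0.025 SD per period. That is about 0.25 T-score points (SD 10) or 0.3 HHIE points (SD 12) per five months.

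**What the adjusted model can show.** The 95% interval for period 4 v 1 is ±1.96 × 0.153 = ±0.30 SD, as wide on each side as the planned effect.

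**The case against.** The section already calls these comparisons exploratory and names the confounding, so what remains is a choice between two exploratory methods for a tertiary objective. That stands, and it caps the importance. Disclosure does not remove an avoidable bias, however.

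Below about 0.025 SD of drift per period, the plan's contrast has the smaller mean squared error, and the adjusted model cannot settle the threshold question either. Both stand and belong in the text.

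The optional linear and quadratic model, or the separate Statistical Analysis Plan cited in section 9.4.1, may already keep time. Neither that plan nor the cited trial's model is in the supplied text. A reader might infer that calendar time is left out; section 9.4.9 is silent on this, and silence does not show omission.

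A reader might also infer that the protocol itself predicts calendar shifts. Section 5.5 says that "if there are any changes implemented in Senior Living during the investigation, they will be implemented across all facilities", but it ties this to the UPMC system, and the three non-UPMC facilities are only monitored. Section 10.1.2 says "this study could be suspended if the Assisted Living Facilities limit non-essential personnel (DCs) from entering the building", which concerns access and predicts no shift in outcomes. These passages make drift possible, not expected. If a permanent shift reached seven of ten facilities from Time 3, the within-facility contrast would carry 0.70 of it on average. The adjusted contrast would carry 0.00 on average over the random order, but with an SD of 0.36 of the shift in any one trial.

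**Conclusion.** The point holds as a modest, cheap improvement. The leading exposure comparison in section 9.4.9 carries a calendar bias of 3d for period 4 v 1 (0.06 to 0.30 SD over the assumed drift range). A model on the same data removes it for effects common to all facilities, at 1 to 14% larger standard errors than the within-facility contrasts. The sizes rest on the section 9.2 correlations, 7.5% churn, equal facility sizes and an assumed drift.

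Two stronger readings are not supported. The series 5, 10, 15, 20 months matches the original four steps, and a reader might infer that 20 months is now wrong and should be 25. Section 7.3 gives a 7 to 8 week collection window but, in the supplied text, does not place it within the period. The fifth exposure period is therefore about 20 to 25 months, and 20 is not shown to be an error. Nor does the primary result suffer: section 9.4.2 already uses categorical time.

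**What to change.** In section 9.4.9, make this the main exploratory exposure analysis: the section 9.4.2 model with the intervention term replaced by indicators for facility exposure periods 1 to 5, keeping categorical time and the same random effects. Report each difference from period 1 with a 95% CI. Keep categorical time in any linear or quadratic exposure model, and present changes from baseline as descriptive.

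Label levels by exposure period and state where the assessment falls within the period, so that months can be attached. Note that period 5 rests on two facilities. State that a non-significant difference between periods will not be reported as a maintained effect, and that shifts confined to some facilities are removed only on average over the randomised order.

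The cost is wording and one extra model, with no new data, plus the precision loss tabulated above (5 to 35% against a pooled model without time). The primary analysis stays as it is. If the separate Statistical Analysis Plan already contains this model, only the protocol wording needs aligning.
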